## 12. DISPOSITION OF SUBJECTS

The number of screened, assigned to treatment and treated subjects, and main reason for discontinuation or no assignment will be provided on the Screened subjects set.

The number of subjects in each analysis set detailed in section 7 (except the Screened subjects set) will be provided overall, and by country and centre on the Full Analysis Set. The number of subjects in the PK Set will be provided only when Pharmacokinetics parameters described in section 19 are analysed (i.e. End-Of-Study analysis).

The number of subjects by time windows will be also tabulated for the FAS.

The number and percentage of subjects who discontinued the study treatment will be provided by reasons for discontinuation for the FAS.

The number and percentage of patients who discontinued from the 30 days safety follow-up will be provided by reasons for discontinuation for the FAS. The same analysis will be performed for long-term follow-up discontinuation.

## 13. DEMOGRAPHIC AND OTHER BASELINE CHARACTERISTICS

Before the first study treatment administration, subject's background, medical and surgical history, prior therapies, demographic data, disease characteristics, BRAF mutation data and ECOG PS will be described on the ES and FAS.

If more than 10.0% subjects of the FAS are excluded from the Per Protocol Set, demographic data, disease characteristics and BRAF mutation data will be repeated on the PP Set.

The table below presents the variables that will be described:

**Table 9: Demographics and Baseline Characteristics**

Variable	Quantitative parameters	Qualitative parameters	Derived variable	Formula derivation if applicable
Demographic data				
Gender		X		
Age (years)	X			
Age (EudraCT categorization: 18-64, 65-84, ≥ 85 years old)		X		
Age (categorization: 18-64, 65-74, ≥ 75 years old)		X		
Height (cm)	X			
Weight (kg)	X			
BMI (kg/m  )	X		X	Weight (kg) / [Height (m)]  rounded to 1 decimal place
BSA(m  )	X		X	BSA=W**0.425 x H**0.725 x 0.007184 NB: if calculated, the BSA will be rounded to the first decimal place
Race		X		
Ethnicity		X		
Disease characteristics				
Time since initial diagnosis (days)	X		X	(reference start date - date of initial diagnosis of primary site)
Primary tumor location		X		“Other” modalities reported will be considered into existing category when appropriate. In particular, “caecum” or “cecum” will be considered as “Colon, right” and “sigmoid will be considered as “Colon, left” Rectum location reported as “Other” will be considered as a category.
Time since date of first metastasis (days)	X		X	(reference start date - date of first metastasis)
Number of subjects with metastases at initial diagnosis	X		X	Subjects with Date of initial diagnosis ≤ Date of first metastasis ≤ Date of initial diagnosis + 30 days And no antineoplastic therapy taken between the initial diagnosis and the date of first metastasis
Time from initial diagnosis to first metastasis (days)	X		X	(Date of first metastasis – Date of initial diagnosis)
Stage at study entry		X		
Number of metastatic organs		X		
Metastatic organs		X		
Number of subjects with lung metastases only		X		
MSI Status*		X		
ECOG-Performance Status		X		
BRAF mutation				
Local result		X		
Central result		X		
Other subjects characteristics at baseline				

Variable	Quantitative parameters	Qualitative parameters	Derived variable	Formula derivation if applicable
Baseline CRP level		X		≤ local ULN and >local ULN
Baseline CEA		X		≤ local ULN and >local ULN
Baseline CA19-9		X		≤ local ULN and >local ULN

\* Blood sample for MSI testing (control sample) will not be processed on an ongoing basis during the study, but once for all subjects enrolled. MSI Status will thus remain undetermined during the study and will be described when available (cf. [Appendix 5](#)).

In addition, a separate summary will be generated for the subgroup of subjects in Japan.

▪ **Concomitant diseases and medical and surgical histories**

Number and percentage of subjects with at least one concomitant disease as well as medical and surgical histories (as described in MEDICAL HISTORY / CONCOMITANT DISEASE eCRF page) will be tabulated descriptively using the MedDRA codes of System Organ Classes (SOC) and Preferred Terms (PT).

▪ **Prior antineoplastic therapy**

Number and percentage of subjects with at least one prior antineoplastic therapy since initial CRC diagnosis (including neo-adjuvant), as described in PRIOR ANTI-NEOPLASTIC THERAPY - MEDICATION eCRF page, will be tabulated descriptively overall and, by setting (adjuvant, neo-adjuvant, metastatic, locally advanced, unknown), and best overall response.

Prior Single agent used from the CRC diagnosis (including neo-adjuvant) will be also provided by type of treatment (chemotherapy, chemoradiotherapy, hormonal biologic targeted therapy, other) and therapeutic area according to the WHO-DRUG dictionary using the "anatomical therapeutic chemical" (ATC) classification, by WHO-DRUG ATC2, ATC4 and Preferred Term.

The number of patients with at least one combination identified in Appendix 1 with start dates within the same month or treatments taken in parallel despite being started within the same one month interval will be tabulated.

▪ **Other Prior Medications**

Number and percentage of subjects with at least one prior medication used before signature of any informed consent (as described in PRIOR AND CONCOMITANT THERAPY eCRF page) will be tabulated descriptively. They will be classified by therapeutic area according to the WHO-DRUG dictionary using the "anatomical therapeutic chemical" (ATC) classification, by WHO-DRUG ATC2, ATC4 and Preferred Term.

▪ **Prior procedures**

Number and percentage of subjects with at least one prior therapeutic / diagnostic procedure (as described in MEDICAL AND SURGICAL PROCEDURES eCRF page) will be tabulated by SOC and PT using the MedDRA terminology.

Number and percentage of subjects with at least one prior antineoplastic surgery received prior to study entry (as described in PRIOR ANTI-NEOPLASTIC THERAPY - SURGERY eCRF page) will be tabulated by site, location and treatment intent. Location will be classified as done for primary tumor location (cf. Table 9).

Result of surgery will be described by location (primary site, metastatic site).

Number and percentage of subjects with at least one prior antineoplastic surgery will be also tabulated by SOC and PT using the MedDRA terminology.

The following number and percentage of subjects will be provided:

- with at least one prior antineoplastic surgery associated with an ileostomy or colostomy,
- with at least one prior antineoplastic surgery associated with an ileostomy,
- with at least one prior antineoplastic surgery associated with a colostomy

- with no resection of the primary tumor and with an ileostomy or a colostomy
- with an ileostomy or colostomy ongoing at study entry
- with a permanent ileostomy or colostomy

The time since the creation of the ileostomy or colostomy will be described for stomies that are ongoing at study entry, and the duration of the stomy will be described for stomies that were removed before study entry. The time since the creation of the ileostomy or colostomy will be derived as (reference start date - date of stomy creation).

The number and percentage of subjects with at least one prior antineoplastic therapy (Radiotherapy) used prior to study entry (as described in PRIOR ANTI-NEOPLASTIC THERAPY – RADIOTHERAPY eCRF page) will be tabulated by location, treatment intent (palliative, curative, unknown), treatment setting (adjuvant, neo-adjuvant, metastatic, locally advanced, unknown), procedure linked to Chemotherapy (No/Yes) and Best Overall Response.

## 14. ANALYSIS OF EFFICACY

Efficacy analyses will be conducted using the ES and FAS. A supportive analysis of the primary outcome will be conducted using the PPS.

### 14.1. PRIMARY ENDPOINT: CONFIRMED ORR BASED ON INVESTIGATOR-ASSESSED TUMOR EVALUATION

#### BOCR

The best overall confirmed response (BOCR) will be derived as per RECIST guideline version 1.1.

Only tumor assessments performed before the start of any further antineoplastic therapies (i.e. any additional secondary antineoplastic medication or anti-cancer surgery or radiotherapy) and not later than 30 days after last study treatment administration will be considered in the assessment of BOCR. Clinical deterioration or clinical progression noted on the end-of-treatment eCRF will not be considered as documented disease progression.

The BOCR for each subject is determined from the sequence of overall (lesion) responses according to the following rules:

- CR: at least two determinations of CR at least 4 weeks apart before progression
- PR: at least two determinations of PR or better at least 4 weeks apart before progression (and not qualifying for a CR)
- SD: at least one SD assessment (or better)  $\geq 6$  weeks after start of treatment (and not qualifying for CR or PR).
- PD: early progression  $\leq 9$  weeks after first study treatment administration (and not qualifying for CR, PR or SD).
- NE = all other cases (i.e. not qualifying for confirmed CR or PR and without SD  $\geq 6$  weeks or early progression  $\leq 9$  weeks after first study treatment administration)

Best overall confirmed response will be summarized, with reasons for having unknown status in Non-Evaluable patients, including:

- No baseline assessment, no measurable disease at baseline
- No post-baseline assessment
- All post-baseline assessments have overall response of “NE”
- New antineoplastic therapy (i.e. any additional secondary antineoplastic medication or anti-cancer surgery or radiotherapy) started before first post-baseline assessment
- Unconfirmed CR, PR or SD with first adequate assessment < 6 weeks Progression >9 weeks after first study treatment administration

The following table, based on Table 3 from the RECIST 1.1 guidelines, summarizes the algorithm describing how Best Overall Confirmed Response (BOCR) is determined from the overall tumor assessments. The order used to determine the BOCR is CR>PR>SD>PD, ignoring visits with missing tumor assessments.

All assessments following an assessment of PD will be excluded from the derivation of BOCR.

**Table 10: Best Overall Confirmed Response**

Case	Best Overall response		BOCR
	First timepoint	Subsequent timepoint	
1	CR	CR	CR (if assessments at least 4 weeks (28 days) apart). (note: sequence of CR – NE – CR would be considered as confirmed CR)
2	CR	PR	SD, PD or PR 
 
• If a CR truly met at first timepoint, any subsequent assessment of PR should make the disease PD at that point. That is, neither a PR nor SD may follow CR
 
• Therefore, SD, if CR assessment ≥ 6 weeks, i.e. 42 days after date of first administration of study treatment,
 
• otherwise PD.
 
 However BOCR may be PR if subsequent scans suggests small lesions were still present at first time point (in

Case	Best Overall response		BOCR
	First timepoint	Subsequent timepoint	
			which case first assessment of CR should be changed to PR)*
3	CR	SD	SD or PD 
 
• SD, if CR or SD assessment <math>\geq</math> 6 weeks, i.e. 42 days after date of first administration of study treatment,
 
• otherwise PD
 

4	CR	PD	SD or PD 
 
• SD, if CR assessment <math>\geq</math> 6 weeks, i.e. 42 days after date of first administration of study treatment,
 
• otherwise PD
 

5	CR	NE	SD or NE 
 
• SD, if CR assessment <math>\geq</math> 6 weeks, i.e. 42 days after date of first administration of study treatment,
 
• otherwise NE
 

6	PR	CR	PR (if assessments at least 4 weeks (28 days) apart).
7	PR	PR	PR (if assessments at least 4 weeks (28 days) apart). (note: sequence of PR – NE – PR would be considered as confirmed PR)
8	PR	SD	SD or PD 
 
• SD, if PR or SD assessment <math>\geq</math> 6 weeks, i.e. 42 days after date of first administration of study treatment,
 
• otherwise PD
 

9	PR	PD	SD or PD or NE 
 
• SD, if PR assessment <math>\geq</math> 6 weeks, i.e. 42 days after date of first administration of study treatment,
 
• otherwise PD if PD assessment <math>\leq</math> 9 weeks, i.e. 63 days after date of first administration of study treatment,
 
• otherwise NE
 

10	PR	NE	SD or NE 
 
• SD, if PR assessment <math>\geq</math> 6 weeks, i.e. 42 days after date of first administration of study treatment,
 
• otherwise NE
 

11	SD	SD	SD
12	SD	PD	SD or PD or NE

Case	Best Overall response		BOCR
	First timepoint	Subsequent timepoint	
			
 
• SD, if SD assessment <math>\geq</math> 6 weeks, i.e. 42 days after date of first administration of study treatment,
 
• otherwise PD if PD assessment <math>\leq</math> 9 weeks, i.e. 63 days after date of first administration of study treatment,
 
• otherwise NE
 

13	SD	NE	SD or NE 
 
• SD, if SD assessment <math>\geq</math> 6 weeks, i.e. 42 days after date of first administration of study treatment,
 
• otherwise NE
 

14	NE, -	SD	SD or NE 
 
• SD, if SD assessment <math>\geq</math> 6 weeks, i.e. 42 days after date of first administration of study treatment,
 
• otherwise NE
 

15	CR, PR, SD	-	SD or NE 
 
• SD, if assessment <math>\geq</math> 6 weeks, i.e. 42 days after date of first administration of study treatment
 
• otherwise NE.
 

16	PD		PD or NE 
 
• PD if PD assessment <math>\leq</math> 9 weeks, i.e. 63 days after date of first administration of study treatment,
 
• otherwise NE
 
 Ignore all assessments after initial overall response of PD.
17	NE	NE	NE Where all assessments are Not evaluable

\* As per Table 3 from RECIST guideline (version 1.1).

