17.6.5. Time point response

It is assumed that at each protocol specified time point, a response assessment occurs table 1 provides a summary of the overall response status calculation at each time point for subjects who have measurable disease at baseline.

Table 1- Time point response: subjects with target (± non-target) disease.			
Target lesions	Non-target lesions	New lesions	Overall response
CR	CR	No	CR
CR	Non-CR/non-PD	No	PR
CR	Not evaluated	No	PR
PR	Non-PD or not all evaluated	No	PR
SD	Non-PD or not all evaluated	No	SD
Not all evaluated	Non-PD	No	NE
PD	Any	Yes or No	PD
Any	PD	Yes or No	PD
Any	Any	Yes	PD

CR=complete response, PR=partial response, SD=stable disease, PD=progressive disease, NE=not evaluable

- **Missing assessments and not evaluable designation**

When no imaging/measurement is done at all at a particular time point, the subject is not evaluable (NE) at that time point. If only a subset of lesion measurements are made at an assessment, usually the case is also considered NE at that time point, unless convincing argument can be made that the contribution of the individual missing lesion(s) would not change the assigned time point response. This would be most likely to happen in the case of PD.

- **Best overall response: all time points**

The *best overall response* is determined once all the data for the subject is known.

Best response is defined as the best response across all time points (for example, a subject who has SD at first assessment, PR at second assessment, and PD on last assessment has a best overall response of PR). When SD is believed to be the best response, it must also meet the protocol specified minimum time from baseline. If the minimum time is not met when SD is otherwise the best time point response, the subject's best response depends on the subsequent assessments. For example, a subject who has SD at first assessment, PD at second and does not meet minimum duration for SD, will have a best response of PD. The same subject lost to follow-up after the first SD assessment would be considered not evaluable.

- **Special notes on response assessment**

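### The SAP classes documented progression after day 63, with no earlier qualifying CR, PR or SD, as Not Evaluable, whereas the protocol's RECIST appendix makes it PD

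*SAP*

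**What the plan says.** SAP 14.1 opens with the statement "The best overall confirmed response (BOCR) will be derived as per RECIST guideline version 1.1". Its rule list then reserves PD for progression no later than 9 weeks after first dose "and not qualifying for CR, PR or SD", and sends every remaining subject to NE. Among the reasons for NE status that are to be tabulated it names "Progression >9 weeks after first study treatment administration".

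Table 10 carries this through:
- Case 12 (SD, then PD): SD if the SD scan is at 42 days or later; "otherwise PD if PD assessment" is within 63 days; otherwise NE.
- Case 9 (PR, then PD): the same ladder.
- Case 16 (PD as the first result): PD within 63 days, otherwise NE, with the instruction "Ignore all assessments after initial overall response of PD".

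SAP 14.2.2 and Table 11 (cases 3 and 4) repeat the cut-off for confirmed plus unconfirmed response. SAP 14.2.1 and 14.2.3 apply both derivations to the central review.

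The protocol's RECIST appendix (17.6.5) states the general rule "Best response is defined as the best response across all time points". It also works an example: a subject with "SD at first assessment, PD at second and does not meet minimum duration for SD, will have a best response of PD". No latest date is attached to the PD. At subject level, its example of a not-evaluable best response is loss to follow-up after an SD that came too early.

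**The concern.** A subject with documented radiological progression is a treatment failure, not a subject without information. The SAP says it follows RECIST 1.1, but it gives some of these subjects a different best response from the one in the protocol's own appendix. In the local and central best-response tables the PD row would be too low and the NE row too high. The descriptive summaries of CEA and CA19-9 change by best confirmed response (SAP 17) would carry the same misclassification. The protocol contains no 9-week limit, and SAP section 20 does not list one among the changes from the protocol.

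**Working it through.** **Inputs.** The minimum time for SD is 42 days and the latest PD is 63 days (SAP 14.1, Table 10). Scans are every 6 weeks for 12 weeks, ±7 days (protocol 8.1 and 9.1.6). The second scheduled scan is therefore due on day 84 ± 7, that is day 77 to 91, which is always later than day 63.

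**Both rules applied to the same scan sequences** (days after first dose):

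| Sequence | SAP | Protocol 17.6.5 |
|---|---|---|
| SD 38, PD 84 | NE | PD |
| SD 41, PD 84 | NE | PD |
| NE 42, PD 84 | NE | PD |
| PD only, at 64 or 84 | NE | PD |
| PR 38, PD 84 | NE | PD |
| SD 42, PD 84 | SD | SD |
| SD 38, PD 60 | PD | PD |
| PD only, at 42 or 63 | PD | PD |

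The first two rows match the appendix's worked example. The next two follow from its general rule, because PD is the only evaluable result. The PR row follows because an unconfirmed PR cannot stand as best response (protocol 17.6.4) and the minimum time for SD is not met.

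**Consistency within the SAP.**
- Table 10 case 4 (CR before day 42, then PD) gives PD with no 63-day limit, unlike cases 9, 12 and 16.
- SAP 14.1 says visits with missing assessments are ignored when the responses are ranked. A missed first scan followed by PD should then rank as PD, but case 16 makes it NE if the PD falls after day 63.
- In the example under Table 8 (SAP 9.3, scenario 2), SD on day 21 and PD on day 76 is an uncensored PFS event. Under Table 10 case 12 the same subject has SD before day 42 and PD after day 63, so the best response is NE.

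**Effect on the primary analysis.** cORR = (confirmed CR + confirmed PR)/N, with N the whole analysis set (SAP 14.1). PD and NE are both non-responses within N, so relabelling one as the other changes neither numerator nor denominator. The design figures can be reproduced without any PD or NE count. With X1 ~ Bin(40, p) and X2 ~ Bin(50, p), the probability of rejecting is the sum over x = 12 to 40 of P(X1 = x) × P(X2 ≥ 37 − x):
- p = 0.30: 0.0161 (stated 1.6%)
- p = 0.45: 0.798 (stated 80%)

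**Size per subject.** Each affected subject moves 1/90 = 1.1 percentage points from PD to NE in a table of 90.

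**The case against.** The cut-off was deliberate. The SAP version log says the derivation was aligned with previous studies so that PD captures early progression. Protocol 13.1 lets the SAP modify methods, and requires an amendment only for major changes to the primary outcome, which this is not. The appendix is largely generic RECIST text and says that early progression and inevaluability are study specific. Late progression is a named NE reason in both 14.1 and 14.2.2, so a reader of the planned tables could add these subjects back. No endpoint is a PD rate or a disease-control rate, and PFS handles progression under its own rules.

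Much of this stands, and it keeps the point small. It does not reconcile the texts. The appendix expects study-specific conditions to be described in the protocol, and they are not. A rule carried over from other studies still disagrees with the worked example in this protocol. A footnoted reason does not correct the PD and NE rows themselves.

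The first-scan window also limits how often the explicit example can occur. Protocol 8.1 gives day 42 ± 7, so SD on day 35 to 41 would be in window. The protocol flow-chart, protocol 9.1.6 and SAP 9.3 allow only day 42 + 7, which makes such a scan early. A missed or NE first scan followed by PD at week 12 triggers the rule under either window.

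A reader might infer that every subject with a missed, NE or early first scan who later progresses is labelled NE. The documents do not support that. Progression documented by day 63 stays PD, and protocol 8.1 allows additional imaging when progression is suspected. An assessment of SD or better at or after day 42 gives at least SD.

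**Conclusion.** The conflict is real and narrow. It is explicit for case 12, where the protocol gives the same sequence and the opposite answer. For case 16, and for an NE first scan followed by PD, it rests on the appendix's general rule. It affects only subjects whose first scan was missed, NE or before day 42, who have no later qualifying response or SD, and whose progression is first documented after day 63. The direction is certain: PD can only be understated and NE overstated.

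The number affected is unknown and probably small. The documents give no rate of missed, unevaluable or early first scans, so no count or percentage can be attached. Nor do they support reading this as a bias in the primary result or as concealment of failures: cORR, its denominator and the 11/40 and 37/90 rules are unchanged, and late progression is listed as a reason for NE. What changes is the PD/NE split in the local and central best-response tables and the exploratory CEA/CA19-9 summaries by best confirmed response.

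**What to change.** Remove the 9-week limit from the PD and NE definitions in SAP 14.1 and 14.2.2, from Table 10 cases 9, 12 and 16, and from Table 11 cases 3 and 4. Define PD as any documented progression in a subject not qualifying for CR, PR or SD. Keep the SAP's existing window for all categories: before any new antineoplastic therapy and not later than 30 days after last study treatment. Without that window, PD would be counted over a longer period than CR, PR or SD. Delete "Progression >9 weeks after first study treatment administration" from both lists of NE reasons. The central-review tables follow by reference.

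The cost is SAP wording, a small derivation change and a slightly higher reported PD percentage. If the sponsor prefers to keep the convention, the minimum is to state it in the protocol as a departure from the RECIST appendix, list it in SAP section 20, and report late PD on its own row, apart from true NE.

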**Confirmed objective response rate**

The **confirmed objective response rate** will be defined as the sum of confirmed CR and PR rate:

$$\text{cORR} = \frac{\sum (\#CR + \#PR)}{N}$$

with:

- # CR = number of subjects with a best confirmed complete response
- # PR = number of subjects with a best confirmed partial response.
- N = number of subjects in the analysis set.

